# WEARABLE SENSOR DRIVEN CLOSED-LOOP DEEP BRAIN STIMULATION

#### NCT03051178

#### **Investigators:** [name], University of Florida, Biomedical Engineering [name], University of Florida, Neurology

Background: The clinical value of a smarter deep brain stimulation (DBS) system that responsively stimulates when pathologic symptoms are present, or adaptively modifies stimulation parameters to match the degree of pathology has been long recognized within the neuromodulation community[1]. Continuous, or open-loop DBS may not be necessary for disorders that are paroxysmal. Hence, intermittent DBS delivered only when pathological activity is present might be equally effective and decrease adverse events. Compared to intermittent stimulation on demand, continuous DBS results in unnecessary disruption of normal brain function and has been linked to serious side effects including dysarthric speech and dysphasia[2], [3]. Open-loop DBS also results in rapid battery depletion necessitating frequent surgery for pulse generator replacements. Hence, closed-loop DBS has been hypothesized to have the following potential advantages compared to open-loop DBS: i) the provision of a better and tailored approach for individual patients, ii) the ability to address the paroxysmal symptoms, iii) reduced adverse side effects, and iv) prolonged battery life (fewer number of battery replacement surgeries). The proof-of-concept of these hypotheses, however, has been lacking and the clinical efficacy of closed-loop DBS remains to be demonstrated in movement disorders.

The overall purpose of this application is to capture pathological activity related to essential tremor using external wearable sensors to responsively initiate or terminate DBS. To this end, we propose to use the Nexus-D system, which can communicate with an Activa implantable neurostimulator (INS), and it will, in a smart way, turn DBS on/off in patients. We will recruit subjects with Activa SC, PC, or RC implants during 6 post-operative programming visits. We will ask patients to perform a baseline visit, where they will be asked to perform tasks (detailed below) the day before their surgery. They will also have the option to participate after the initial six post-operative programming visits. Our research group is already familiar with and is in possession of the Nexus-D system, and we have successfully performed responsive DBS in two patients with Tourette syndrome (TS) and in four patients with Parkinson's disease (PD) in acute settings. Our lab is also equipped with wireless wearable sensor and amplifier systems, such as a 16-unit wireless EMG+ acceleration+inertia Trigno Wireless Bioacquisition System (Delsys Inc, Natick, MA). We aim to combine these signal modalities to capture pathological symptoms and generate commands to initiate or terminate DBS (also record adverse side effects, if any). Our goal is to characterize the clinical efficacy, side effect profile, and battery life of closed-loop DBS in acute settings using wearable sensors in essential tremor patients.

We received an educational grant from Medtronic in 2015 to support a senior design project entitled "Integration of Wearable Sensors to Medtronic Nexus-D for Closed-Loop Deep Brain Stimulation" this past academic year, and the senior design team successfully developed a graphics user interface and platform for our sensors to communicate with Medtronic Nexus-D. Their final design review was approved by Medtronic Liaison Engineers: [name] and [name]. We are now seeking approval to conduct a clinical feasibility and safety study in 20 patients with intention or kinetic tremor in essential tremor (i.e., patients with essential tremor who do not tremor at rest). To adequately capture the side effect profile, we will be recruiting 10 in-clinic ET-DBS patients along with the 20 pre-DBS ET patients to undergo speech testing between open-loop, closed-loop, intermittent, and sham stimulation. Closed-loop DBS is hypothesized to decrease adverse side effects associated with continuous DBS, and ET patients, speech impairments such as dysarthria, are prevalent after DBS[4]–[6]. However, there has been only one study that quantified speech side effects between open-

<sup>1 [contact]

<sup>2 [contact]

loop and closed-loop, but this was conducted in PD patients with externalized leads in the acute setting[7]. Thus, the need to quantify these effects both in ET patients and across clinical populations is imperative.

**Summary of Methodology:** This is a preliminary pilot investigation that will utilize a within subject study design and will enroll 20 DBS patients with ET, who will receive DBS implants as part of standard care for ET. The implantation surgery is not part of the study. We will compare the effectiveness and safety of the standard chronic continuous stimulation mode to the novel acute closed-loop stimulation mode. We will assess both effectiveness and safety of closed-loop stimulation. We will employ blinded video reviews of a validated motor outcome scales, but will also employ objective physiological measures of motor dysfunction in all areas. Additionally, we will enroll 10 in-clinic (i.e. already had a lead placed) DBS patients with ET along with the 20 undergoing to quantify the effects of different stimulation paradigms on speech, namely open-loop, closed-loop, sham, and intermittent stimulation. Sham stimulation will be delivered within clinician limits.

**Sample size:** This will be a pilot study designed to assess the feasibility, safety and potential effectiveness of novel stimulation patterns. We will enroll 20 ET patients with kinetic or intention tremor scheduled for DBS implants (Activa SC, PC or RC) in the Vim over the course of 3 years. The study was designed to utilize each patient as their own control, and to compare results against the performance of motor symptoms versus open-loop DBS. UF has implanted 27 ET patients with Activa SC in 2014 alone. The feasibility of recruiting 20 subjects in 3 years therefore is very high. These patients will all receive these implants as standard of care and the only difference will be the trial of responsive DBS. Additionally, we will enroll 10 DBS patients with ET in- clinic along with the 20 closed-loop patients to quantify the effects of different stimulation paradigms on speech, namely open-loop, closed-loop, no stimulation, and intermittent stimulation. There are on average 2-8 ET-DBS patients in clinic every week. Therefore, the feasibility of recruiting 10 patients for a one-day study is high.

### **Research Plan:**

For the first 6 months post-DBS surgery, subjects will participate in the research after their monthly clinical programming visit. Subjects may still be recruited several months after they have received DBS and still participate in the 6-month outcomes, however, these subjects will not have a research visit after a monthly programming visit. Their visits will be scheduled with the researcher. Additionally, if an already recruited subject undergoes surgery for the contralateral side, these subjects may provide consent again and closed-loop DBS will be tested on the contralateral side. Their research visits will happen after their monthly clinical programming visits or scheduled with the researcher. Subjects who provide consent again will participate in 12 research visits altogether. Stimulation parameters will be empirically derived for each research subject by a movement disorder specialist. These optimized parameters will be used for open- and closed-loop stimulation trials. Baseline tremor severity will be assessed using the following assessments:

- Fahn, Tolosa, Marin Tremor Rating Scale (TRS): This 5-point scale rates tremor severity based on tremor amplitude, from 0 (no tremor) to 4 (severe tremor) in each part of the body and includes assessments of specific abilities and functional disabilities
- Quality of Life in Essential Tremor (QUEST): This is a 30-item assessment that has 5 options for the patient including Never/No, Rarely, Sometimes, Frequently, and Always/Yes. The questionnaire also contains additional items including the sexual function, current work status and satisfaction with medications for tremor control and any side effects from the medication.

The recordings from the first and second research visits will be used to delineate rest from tremor. This will serve as the control feature for stimulation and detector validation. During visits 3-6, the output of the tremor detector will be used to provide acute responsive stimulation.

Subjects will complete all tasks in the protocol from a comfortably seated position. The study

will be videotaped in its entirety, and rated by a blinded movement disorders neurologist. The following clinical data will be gathered from the patient and/or medical record:

- name,
- age,
- gender,
- race,
- phone number,
- diagnosis,
- stage,
- age at onset,
- past neurological medical history
- imaging performed as part of your DBS surgery (MRI, CT, etc)
- Records of past physical exams, treatments, evaluations, and any other procedures you may have done for ET
- Responses to ET questionnaires
- neurological assessments performed during the Fast Track appointment as part of your DBS surgery assessment,
- records about study devices
- pre-DBS off-medication ET scales, and current DBS settings.
- Programming visit dates

**Figure 1.** Experiment setup for recording EMG and inertia data during movement intention and tremor. Patient will be cued to pick up an object with the flashing of a red LED light (top). They will reach and grasp the object once the green LED on the same object lights up (bottom). In this setup, the patient will use the hand closer to the object (contra- or ipsilateral to the implant). During the next stage of experiments, they will perform volitional reach and grasp movements (i.e., without LED cues).

Figure 2. Example of the placement for the EMGs on the patient's arm

We will utilize the Direct Instrumented Measurements of Tremor Severity developed by our team to study the relationship between EMG, inertia data and tremor. A summary of this system includes the Activa SC or PC neurostimulator, the Nexus-D wand to stream data onto a computer, wireless sensors for EMG and inertia (Delsys, Inc., Natick, MA), a camera to capture behavioral activity, and 4-6 objects, each object with a red and green LED and accelerometers (Figure 1). The subject will sit in front of a table with the various objects distributed equally to the two halves of the table. The patient will wear wireless EMG and acceleration sensors on several muscles within the upper extremity (Figure 2). A red LED will light up on one of the objects, identifying it as the target object. The patient will be instructed to wait until the green LED on the target object lights up, signaling them to reach and grab the object. The time between the cue (red LED) and go signal (green LED) will be between 1-2 secs. The patient will be instructed to reach out with the hand closest to the target object. The end of each trial will be determined from inertial sensor on the target object. Subjects will repeat this task 5 times with rest periods of 1-2 mins in between. This first experiment and placing the sensors will last about 1.5-2 hours.

The time between the cue and go instructions will be labeled as the "intention" period. We will use these periods to extract EMG features of movement intention. We will do so by comparing the spectral content of intention periods to inter-trial intervals (i.e., rest condition), and statistically verify the significance of modulations using randomization tests. We will further utilize this biomarker of movement intention in offline linear discriminant analysis (LDA) on the external computer to develop detector weight coefficients that will be used to control the Activa neurostimulator through Nexus-D. We will first investigate the performance of the event detector, without using the output of the detector for responsive stimulation. We will use the metric measure sensitivity to optimize the weights. Sensitivity is the ratio of true positives detected (correct detections) over the sum of true positives and false negatives (missed events). This metric penalizes failures to detect intention to move, but does not penalize false positives, as the latter would merely lead to an unnecessary responsive stimulation. Since these patients would otherwise be receiving continuous stimulation, a few falsely initiated stimulations should be tolerable. The weights will be optimized until a satisfactory sensitivity measure that would lead to a tolerable and therapeutic number of stimulations in a responsive stimulation scenario is reached.

To test the system in a more natural setting, we will conduct a second set of experiments where

subjects will volitionally pick any object of their choice. All LEDs will turn red to cue the patient and then green to instruct them to reach and grab the object of their choice. Patients will repeat this task 5 times with rest periods of 1-2 mins in between. Additionally, patients will perform tasks of their choosing to mimic daily life activity (eating, reading a book, or putting on a jacket). The experiment will also include tasks pertinent to TRS. These experiments include tasks like finger to nose touching, posture holding with intervals of arms outstretched with wrists extended and arms retracted towards the patient's chest, and drawing an Archimedean spiral. In a final set of experiments, we will ask the patient to walk. This will test the robustness of detection in situ, where DBS should remain inactive in the absence of tremor. This portion of experiments should last between 2-2.5 hours.

These experiments will be repeated in DBS OFF and ON conditions at each study visit (postoperative months 1-6). In responsive DBS, the stimulator will responsively switch to the HIGH setting upon detection of intention to move, or detection of tremor; and will switch to the LOW setting when the signals for intention to move and for tremor are both absent (visits 3-6). To test the tolerability of intermittent stimulation, we will test a duty cycle as follows: active stimulation (HIGH setting) for 4 seconds then switching to the LOW setting for 30 seconds. We will optimize the HIGH and LOW amplitude settings, along with rise and fall times to find a therapeutic setting that is tolerable.

After the visit, battery consumption will be calculated and compared between the open- and closed-loop stimulation conditions. The Medtronic battery estimator helpline will be used to calculate battery life.

Since this is a pilot study, the trial will not be powered as a clinical trial, but instead will be exploratory and the results will be used for a larger clinical trial (efficacy rather than effectiveness).

For patients enrolled in the closed-loop DBS portion of this study, at one of their monthly postoperative research visits, we will test the effects of stimulation on speech. Specifically, we will test open-loop, closed-loop, intermittent, and sham stimulation. Sham stimulation will be delivered within clinician limits. For patients enrolled within the in-clinic speech assessment portion, we will approach them in clinic and perform a one-day assessment of the aforementioned stimulation paradigms on speech. Altogether, 30 individuals will undergo speech testing. We have added intermittent stimulation because we do not believe that closed-loop will be triggered during speech, since the patient is not moving. Speech will be assessed using the following paradigm:

- 1. Participants will be asked to produce a sustained vowel 'ah,' and complete repetition tasks including diadochokinesis (DDK; /p/, /t/, /k/) and 4 sentences:
  - a. In the summer they sell vegetables.
  - b. The shipwreck washed up on the shore.
  - c. Please put the groceries in the refridgerator.
  - d. The valuable watch was missing.

Speech samples will be digitally recorded using a hand-held microphone for offline analysis. Analysis will be completed using PRAAT software (http://www.fon.hum.uva.nl/praat/) to determine duration of sustained vowel phonation,

fundamental frequency, jitter, shimmer, DDK rate, sentence rate, and spectrogram metrics.

**Regulatory approvals:** We will write and obtain approval from the Institutional Review Board (IRB). Informed consent will be obtained from all subjects. Patients will be recruited during routine DBS programming sessions. DBS patients can also be recruited through the INFORM database (IRB approved) and approached over the phone to be informed of the study. The INFORM database is a database in which patients who present to the Movement Disorder clinic agree to be contacted for future research opportunities and have their data stored. These include patients who have undergone DBS. We will recruit 20 Vim DBS patients with

essential tremor for closed-loop testing. An additional 10 will be recruited to quantify the effects of stimulation on speech along with the 20 for closed-loop testing. This is non-significant risk study, as the amount of stimulation delivered will be shortened to times only when the patient is moving.

**Privacy and Confidentiality:** This entire visit will be videotaped for a blinded reviewer to assess the efficacy of the new treatment by rating the severity of your tremor. It is a requirement of the study to be videotaped. We will store this video on a secure network only accessible to research personnel associated with this study. After the study is over, the video will be destroyed.

**Possible Discomforts and Risks:** Participation in the study can cause exhaustion. During stimulation optimization, patients might be exposed to short duration stimulation parameters that are not comfortable. These settings will be noted down and will not be repeated. To minimize the risk of such discomfort during R-DBS, the tolerability of setting parameters will be tested by a clinical programmer through duty cycle stimulation. Usually, it is possible to achieve equivalent clinical benefit by lowering stimulation amplitude and increasing pulse width. The EMG and inertia sensors may cause skin irritability and discomfort.

**Possible Benefits:** This study also has the potential to guide in the development of responsive DBS therapy.

**Compensation:** Subjects will be compensated \$25 for each 6-month post-operative visit or each in-clinic speech assessment and will be offered a one-night hotel stay if needed

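### The second-stage reach task is uncued in the Figure 1 legend but LED-cued in the procedure text; run as cued, it cannot measure detection of self-initiated reaching

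*Combined protocol and SAP*

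**What the plan says.** All of this is in the Research Plan of the combined protocol and SAP.

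- **Figure 1 legend.** After describing the cued task, it says: "During the next stage of experiments, they will perform volitional reach and grasp movements (i.e., without LED cues".
- **Procedure text for the second set.** The stated aim is a test under more natural conditions, and the freedom given to the patient is that "subjects will volitionally pick any object of their choice". The next sentence then sets the timing: "All LEDs will turn red to cue the patient and then green to instruct them to reach and grab the object of their choice". The task is done 5 times, and no cue-to-go interval is given for it.
- **First experiment.** One object is designated as the target, and the task is again done 5 times. The interval is stated here: "The time between the cue (red LED) and go signal (green LED) will be between 1-2 secs".
- **Detector development.** "The time between the cue and go instructions will be labeled as the" intention period, and "We will use these periods to extract EMG features of movement intention". These features feed a linear discriminant analysis whose weights are tuned on sensitivity, defined as true positives over true positives plus false negatives.
- **Other tasks in the same session.** Self-chosen daily activities, tremor-scale tasks and walking are listed, with no mention of LED cues.
- **Use of the detector.** In responsive stimulation the HIGH setting is triggered by detected intention to move or by detected tremor.

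**The concern.** Staff cannot follow both descriptions, and the choice between them decides what the task measures. A reach started on a light has an externally timed waiting period in which the patient already knows a movement is coming. The EMG features of intention are taken from exactly that period. A self-initiated reach may have a shorter or different preparatory phase, so a detector built and checked on cued reaches may do less well when the patient decides when to move.

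The second set is where the plan sets out to check the system under more natural conditions. If its timing is cued, it cannot serve that purpose for the onset of movement. Intention is one of the two triggers for stimulation, and the plan says the results will inform a larger trial. An optimistic impression of anticipatory detection could therefore carry forward unnoticed.

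**Working it through.** The plan states no figure to reproduce, and the point does not depend on sample size or power. The check is a comparison of the text plus a count.

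**Step 1. Do the two descriptions concern the same task?** The second set is the only volitional reach-and-grasp task in the procedure text, and it follows the cued single-target task just as the legend's next stage does. The eating, reading and jacket tasks are introduced separately as additions and are not reach-and-grasp trials on the instrumented objects. The legend and the procedure text therefore describe the same stage.

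**Step 2. What differs?**

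| Feature | Figure 1 legend | Procedure text |
|---|---|---|
| LED signals | none | red, then green, on all objects |
| Choice of object | volitional | volitional |
| Timing of movement | the patient's | set by the LEDs |
| Cue-to-go interval | not applicable | not stated |

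**Step 3. Count of scripted reaches per run, if the procedure text is followed.**

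- LED-timed reaches: 5 (assigned target) + 5 (free choice) = 10.
- Scripted reaches with self-chosen timing: 10 − 10 = 0.
- Reaches with a documented 1-2 s interval: 5, all in the first experiment. This gives 5 × 1 s = 5 s to 5 × 2 s = 10 s of labelled intention recording per run. A similar amount from the second set would require the assumption that it uses the same interval.

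**Step 4. What can be scored?** Sensitivity = TP / (TP + FN), and both terms need a labelled event. The label exists only between cue and go.

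- Cued reaches: TP + FN is defined.
- Uncued movements: no intention event is labelled, so TP + FN = 0 and sensitivity is undefined. This applies to the daily-life tasks and also to the second set as the legend describes it.

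The plan thus lacks a scoring rule under either description. With LEDs, the task does not address self-initiated timing. Without LEDs, it does, but nothing says how to label the event.

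**Step 5. Can onset be labelled with what is there?** The patient wears EMG and acceleration sensors on the arm, the objects carry accelerometers, and the session is videotaped. The plan uses the object's inertial sensor to mark the end of a trial and defines no onset. The signals needed are already recorded; only the definition is missing.

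**The case against.** The strongest reply is that this is a wording conflict in an exploratory, unpowered pilot. Free choice of object is already more natural than an assigned target, and a known cue gives cleaner event labels. The session also includes uncued activities, and a missed intention need not leave the patient without a response, because tremor is a second trigger. Sensitivity is described as a tuning criterion and not as an outcome. The Statistical Analysis section covers tremor-scale scores and hand acceleration and does not say that either comes from the LED reaches.

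Much of this stands, and it rules out several stronger readings that a reader might infer:

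- **That every reach carries a 1-2 s warning.** The interval is documented only for the first experiment.
- **That the detector itself is warned.** The LEDs signal the patient, and nothing says their signal reaches the detector. Any advantage lies in the externally timed preparation present in the EMG.
- **That the two reach tasks are identical.** They differ in who chooses the target.
- **That the protocol never records self-initiated movement.** The daily-life tasks appear uncued. The narrower truth is that they have no stated onset or intention label.
- **That the responsive-stimulation results are biased.** No link from the LED reaches to the planned analyses is documented, and the tremor trigger may limit any effect on stimulation.

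The reply does not remove the contradiction. Nor does it supply a way to score detection of self-initiated reaching.

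**Conclusion.** The concern holds in this limited form. The two descriptions of the second set contradict each other and must be reconciled. If the procedure text is followed, all 10 scripted reaches per run are externally timed, and intention sensitivity can be scored only for cued movements. Detector performance in the reach task intended to be more natural may then overstate performance for self-initiated reaching.

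The direction rests on the assumption that cued preparation is easier to detect in the EMG than self-initiated preparation. That is plausible but not established in the documents. They contain no cued or uncued detection rates, so any percentage-point estimate of the gap would be invented. The change is worth making because it determines whether the study can say anything about anticipatory detection in natural use. It does not call the planned comparisons across stimulation conditions into question.

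**What to change.** 1. Amend the procedure text to agree with the Figure 1 legend: in the second set give no LED signal and let the patient choose when to start.
2. Define movement onset from the arm sensors and object accelerometers already used. Label a window of fixed length before onset as intention, with the length set before the recordings are analysed. Apply the same arm-sensor rule to the daily-life tasks.
3. Summarise sensitivity and detection latency relative to onset separately for cued and uncued movements. Base any statement about natural use on the uncued figures.
4. If the LEDs are kept, correct the legend, describe the task as free target choice with cued timing, state its cue-to-go interval, and draw no conclusion from it about self-initiated reaching.

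The cost is small: LEDs left off for 5 trials per run, and offline labelling from existing recordings. The downside is that sensor-defined onsets are slightly noisier labels than a known cue time.

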Adverse Event Reporting: Once a subject is enrolled into the study, continuous close monitoring will be conducted by the Principal Investigator (PI) in conjunction with the Co-PI and other investigators as well as the University of Florida's Institutional Review Board (IRB), through annual reports of progress and by immediate notification of serious and unanticipated adverse events by the PI to the IRB.

Stopping rules for the study have been established: This study will be suspended by the DSMB only if an unexpected and severe neurological complication occurs and they deem suspending or stopping the study appropriate. Specific examples that would warrant suspending the study include the following, only in the event that they do not reverse with adjustment or discontinuation of the therapy:

- worsening of symptoms
- neurological events such as changes in memory, cognition, and motoric or sensory modalities (the exception to this would be persistent dysarthria, which has been reported with PD and may be an acceptable side effect if symptoms are diminished.

**Statistical Analysis:** All statistical analyses will be performed in R 3.5.2. TRS scores and hand acceleration measures across different stimulation conditions (off, cDBS, rDBS) were assessed using a mixed model ANOVA with the participant as a random effect. All post-hoc comparisons were Bonferroni corrected. Equivalence testing was performed using two one-sided tests. Epsilon, or the region of similarity, for total TRS, contralateral TRS, or hand acceleration were 2 points, 1 point, and 0.1 m/s, respectively.

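### Motor equivalence of rDBS and cDBS: condition order is not controlled and the analysed visits are not stated, although responsive stimulation is recorded only at visits 3-6

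*Combined protocol and SAP*

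**What the plan says.** The motor comparison is within patient (Summary of Methodology; Sample size). On timing, Research Plan says "These experiments will be repeated in DBS OFF and ON conditions at each study visit (postoperative months 1-6", and separately "During visits 3-6, the output of the tremor detector will be used to provide acute responsive stimulation". Visits 1 and 2 serve to develop the detector. For most participants the visits track clinical care: "subjects will participate in the research after their monthly clinical programming visit". Late-recruited subjects are scheduled separately, and a subject who consents again for the second side has 12 research visits in all.

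Under Statistical Analysis, TRS scores and hand acceleration across off, cDBS and rDBS "were assessed using a mixed model ANOVA with the participant as a random effect". Then: "Equivalence testing was performed using two one-sided tests". The margins for that test come next: "Epsilon, or the region of similarity, for total TRS, contralateral TRS, or hand acceleration were 2 points, 1 point", with 0.1 m/s² for acceleration. The pair tested is not named; I take it to be rDBS against cDBS, the comparison that Summary of Methodology sets out.

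No section gives an order of conditions, a randomised or balanced allocation of order, an interval between conditions, or a period, sequence or visit term. The rests of 1-2 minutes separate task repetitions, not stimulation conditions. For speech, "at one of their monthly postoperative research visits, we will test the effects of stimulation on speech" under four paradigms, again without a stated order, and Statistical Analysis names no speech model.

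**The concern.** When each patient is their own control, control of order is what keeps time effects out of the treatment difference. Such effects are plausible here. The two blocks of experiments add up to 1.5-2 h plus 2-2.5 h, or 3.5-4.5 h (whether that covers one condition or all of them is not stated), and the risk section itself warns of exhaustion. Between visits, repeated clinical programming could change tremor under stimulation.

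rDBS has no data at visits 1-2, while OFF and ON do. Unless the analysis is confined to visits where all three conditions were run, condition is partly confounded with visit.

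The equivalence margins are narrow, so a bias of a fraction of a margin matters. Depending on its direction, it can produce a false claim of equivalence or hide a true one. The results are meant to feed a larger trial.

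**Working it through.** The plan gives no alpha, SD, drift or power figure, so there is nothing to reproduce. Documented inputs are n=20, the margins and the visit schedule; everything else below is assumed.

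**1. Fixed order.** With 20 participants, 3 conditions and 3 periods, a model with participant, condition and period has 20 + 2 + 2 = 24 columns. If every participant has the same order, its rank is 22: the condition and period columns coincide, and no later period term can separate them. Drift between the cDBS and rDBS periods then adds one-for-one to their difference.

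**2. Effect on the equivalence test.** Assume a paired two one-sided test at one-sided alpha 0.05, a margin of 1 point and 0.25-point drift favouring rDBS. Equivalence is declared when |mean difference| + 1.729 × s/√20 < 1.

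Hand check at SD 1.5: SE = 1.5/4.472 = 0.335, and 1.729 × 0.335 = 0.580, so the mean must fall below 0.420. With a true loss at the margin and the drift, the mean is centred at 0.75: (0.420 − 0.75)/0.335 = −0.98, or about 16%. Simulation (400,000 draws), which also lets s vary, gives:

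| SD of paired difference | False equivalence, no drift → 0.25 drift | Chance of equivalence when the true difference is 0, no drift → 0.25 drift |
|---|---|---|
| 1 | 4.9% → 28.5% | 99.2% → 94.4% |
| 1.5 | 5.0% → 17.6% | 78.0% → 66.9% |
| 2 | 4.6% → 11.9% | 39.4% → 34.4% |
| 3 | 0.9% → 1.4% | 2.6% → 2.4% |

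Only ratios to the margin matter, so the same figures apply to total TRS (drift 0.5; SD 2, 3, 4, 6) and to acceleration (drift 0.025; SD 0.10, 0.15, 0.20, 0.30 m/s²).

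**3. Pooling all six visits.** Take ON at visits 1-2 as cDBS. Mean visit is (1+2+3+4+5+6)/6 = 3.5 for OFF and cDBS, and (3+4+5+6)/4 = 4.5 for rDBS. Let the outcome change by b per visit, with no true rDBS-cDBS difference.

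- No visit term: bias = (4.5 − 3.5) × b = 1.0 × b.
- Additive visit term, all three conditions changing equally: bias 0.
- Additive visit term, OFF flat, cDBS and rDBS both equal to OFF + D + b × visit. The model compares each condition with the mean of OFF and cDBS at the same visit. For rDBS (visits 3-6) this is (D + 4.5b)/2; for cDBS (visits 1-6) it is (D + 3.5b)/2. The difference is 0.5 × b.
- Visits 3-6 only: bias 0 in both cases.

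Least-squares fits gave the same four values. A per-visit change of 0.25 point thus gives a bias of 0.25 point with no visit term and, if only stimulated tremor changes, 0.125 point with one.

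**4. Repeated visits with a participant intercept only.** Suppose the condition effect varies between participants (assumed participant-by-condition SD 1, residual SD 1) and four visits are used. The variance of a participant's mean difference is 2×1 + 2×1/4 = 2.5. The model with participant, condition and visit has 240 − 25 = 215 residual degrees of freedom. Of these, 19 × 2 = 38 have expected mean square 4×1 + 1 = 5, and the other 177 have 1. The residual variance is therefore (38×5 + 177)/215 = 1.71, which implies 2 × 1.71/4 = 0.85 in place of 2.5. The SE is too small by √(0.85/2.5) = 0.58, and false equivalence is about Φ(−1.65 × 0.58) = 17%. Simulations put it at about 11% for participant-by-condition SD 0.5 and 17-18% for SD 1. A paired test on participant means stays near 5%.

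**5. Limit of balancing.** Balanced orders plus a period term removed linear drift of 0.25 or 0.5 per period: false equivalence was 4.8-5.0%. If rDBS alone leaves a 1-point carry-over, the contrast is still biased by 0.33 point (0.35 at n=20). Equal carry-over from cDBS and rDBS cancels.

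**The case against.** The strongest reply is that neither bias is shown to exist. A reader might infer that OFF, cDBS and rDBS were always run in that sequence, or that visits 1-6 were pooled. The documents say neither. Visits 1-2 are assigned to detector development. Research Plan mentions outcomes at six months, and the DSMB section refers to a primary assessment six months after operation. If the motor comparison uses visit 6, or visits 3-6, the visit bias is nil. This stands, and it makes both parts of the point conditional. But Statistical Analysis is not tied to the six-month assessment and does not say which visits it uses.

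It may also be said that the study is an exploratory pilot without power, and that imprecision matters more than order at large SDs. The SD 3 row above supports that. Pilot status excuses low precision; it does not excuse an avoidable bias in a formal equivalence test with set margins.

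Blinding is a partial answer only. The study "will be videotaped in its entirety, and rated by a blinded movement disorders neurologist", which protects against rater bias, but the tremor being rated can itself differ by period or visit.

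Finally, 13 of 20 closed-loop patients had been recruited when the timeline was written, and the analysis text is partly in the past tense, so prospective balancing may come too late. That limits the first remedy below, not the others.

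**Conclusion.** The point holds in conditional form and should be acted on, at a weight suited to a pilot. The plan leaves condition order uncontrolled, leaves the analysed visits unstated, and names a model that corrects for neither.

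Under a fixed order the bias equals the drift between the cDBS and rDBS periods and cannot be recovered by modelling. Under pooling of all six visits it is 1.0 × b. It is tempting to conclude that a visit term settles the second problem. It does so only if OFF changes as much as the stimulated conditions; if reprogramming changes stimulated tremor alone, half the bias remains.

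The percentages rest on an assumed alpha, SD and drift. They show that a quarter-margin bias matters at SDs of about one to two margins and hardly at all at three. The documents do not establish the direction or existence of any drift, so it cannot be said that the trial's equivalence result is wrong.

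**What to change.** 1. **Remaining sessions at visits 3-6.** Use a pre-generated balanced random order of off, cDBS and rDBS, record it for each session, and keep the interval between conditions the same in every order. The length of the interval is for the investigators to set.
2. **Visits.** State which visits are analysed. Take the rDBS-cDBS contrast from visits 3-6 only, or from the 6-month visit if that is the intended primary assessment. Do not rely on a visit term to rescue a pooled analysis of visits 1-6.
3. **Model.** Run the equivalence test on participant-level mean paired differences, or add a participant-by-condition random effect. Include period as a fixed effect where order varied. Define visit as visit number or postoperative month, and keep second-side visits of re-consented subjects within the same participant.
4. **Completed sessions.** Recover the order from records or videos before the videos are destroyed at study end, as Privacy and Confidentiality foresees. Adjust for period if order varied; if it was fixed, report the contrast as potentially biased by order.
5. **Speech.** Balance the order of the four paradigms in remaining participants in the same way, and state a model with condition and period as fixed effects and participant as a random effect.

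Make no claim of protection against unequal carry-over. If no sessions remain, items 2-4 still apply, as does the model statement for speech.

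The cost is an order list, one field on the session record, a few model changes and a one-off review of records or videos. The downside is slightly more re-setting of the stimulator, a few degrees of freedom, and the loss of visits 1-2 from the contrast.
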